# 10.2 Subject Accountability

The number of subjects screened, enrolled, receiving IP, and completing the study will be summarized. Study discontinuation and IP discontinuation will be tabulated

Statistical Analysis Plan: 20110271

Dated: 26 May 2018 Page 17 of 27

separately by reasons for discontinuation. The number of subjects included in and excluded from each analysis set will be summarized.

## 10.3 Important Protocol Deviations

Important Protocol Deviations (IPDs) categories are defined by the study team before the first subject visit and updated during the IPD reviews throughout the study prior to database lock. If a snapshot is being taken during the study rather than a database lock at the end of the study, categories should be updated during the IPD reviews throughout the study prior to database lock. These definitions of IPD categories, sub-category codes and descriptions will be used during the course of the study. The final IPD list is used to produce the Summary of IPDs table and the List of Subjects with IPDs.

# 10.4 Demographic and Baseline Characteristics

All baseline tables will be summarized by study cohorts for all subjects **in the EAS**, **HAS** and **SAS**. Baseline tables will summarize the following:

- Baseline Characteristics
- Demographics
- Cardiovascular medical history
- Vital signs
- Laboratory parameters
- Fasting Vitamin E
- Lipid-regulating background therapies (eg, statin, ezetimibe)

## 10.5 Analyses of Primary Endpoint

## 10.5.1 General Principles

The Medical Dictionary for Regulatory Activities (MedDRA) version 15.0 or later will be used to code all adverse events (AE) to a system organ class and a preferred term.

**Treatment-emergent AE is defined as in section 6.3**. Severity of AEs will be graded using the CTCAE (Appendix B) and recorded on the eCRF. All adverse event tables will be summarized by actual treatment arm.

Subject incidences of treatment-emergent adverse events (TEAE), serious TEAEs, and TEAEs leading to withdrawal of IP will be tabulated by system organ class and preferred term in descending order of frequency in all subjects. Treatment-related TEAEs will be provided in the overall AE summary.

Statistical Analysis Plan: 20110271

Dated: 26 May 2018 Page 18 of 27

#### 10.5.2 Adverse Events of Interest

Subject incidence of adverse events associated with **injectable protein therapies hypersensitivity reactions or potential hepatitis C infections** will be summarized by category and preferred term **using narrow search strategy**.

# 10.6 Analyses of Secondary and Exploratory Endpoints

# 10.6.1 Analyses of Secondary Endpoints

Descriptive statistics on all endpoints at all scheduled visits and time points will be provided by apheresis status at study entry and by visit including percent change from baseline in the following lipid parameters:

- LDL-C
- non-HDL-C
- Lp(a)
- ApoB
- total cholesterol/HDL-C ratio
- ApoB/ApoA1 ratio
- Number and percent of patients with LDL-C reduction of 15% or greater from baseline by visits will also be provided.

For continuous endpoints, descriptive summaries including group means will be displayed. For response rate analysis, number and percent of responders at each visit will be displayed. All analyses will be performed for the HoFH and severe FH analysis sets unless specified.

Depending on subject's apheresis status, protocol-specified visits vary.

## 10.6.2 Analyses of Exploratory Endpoints

To describe the effects over time of AMG 145 on change from baseline in proprotein convertase subtilisin/kexin type 9 (PCSK9) levels and on change from baseline and percent change from baseline of LDL-C, total cholesterol, non-HDL-C, ApoB, total cholesterol/HDL-C ratio, ApoB/ApoA1 ratio, triglycerides, VLDL-C, HDL-C, ApoA1, Lp(a), and in high sensitivity C-reactive protein (hsCRP), descriptive statistics will be provided by scheduled visits and by apheresis status at study entry. Figures will be provided for change from baseline and percent change from baseline analyses.

A shift table for hsCRP will be provided, for levels at baseline and maximum post-baseline value (< 0.1, 0.1-0.3, > 0.3 mg/dL) by **apheresis status** and genotype (HoFH vs. Non-HoFH).

Statistical Analysis Plan: 20110271

Dated: 26 May 2018 Page 19 of 27

HbA1c will be summarized at each scheduled assessment by **apheresis status** and genotype.

Death, myocardial infarction, hospitalization for unstable angina, coronary revascularization, stroke, TIA, non-coronary revascularizations and hospitalization for heart failure will be adjudicated by an independent CEC. Subject incidence of adjudicated events will be summarized for each **apheresis status** and genotype.

# 10.6.3 Pharmacokinetic or Pharmacokinetic/Pharmacodynamic Endpoints Individual and mean serum AMG 145 and PCSK9 concentration-time profiles by dose group will be provided using nominal times. The effect of apheresis on AMG 145 and pharmacokinetics and also on PCSK9 will be examined separately. Pharmacokinetic data will be analyzed and stored in the Pharsight Knowledgebase Server (PKS) using the current version of Phoenix WinNonlin. Exploratory PK/PD analysis may be conducted separately as part of this study or may be combined with other studies in a meta-analysis.

These analyses will be performed by the PKDM group.

# 10.6.4 Exposure to Other Protocol Specified Treatment

The number and proportion of subjects receiving selected lipid regulating medications captured on the Lipid Regulating Concomitant Medications eCRF will be summarized by **apheresis status** and genotype. Summaries will be provided for baseline use and use after study enrollment. The subject incidence of changes in lipid regulating medications during the treatment period will also be provided.

## 10.6.5 Exposure to Concomitant Medication

The number and proportion of subjects receiving non-lipid regulating concomitant medications will be summarized by preferred term for each defined group as coded by the World Health Organization Drug (WHODRUG) dictionary. Summaries will be provided for baseline use and use after Study Day 1 OL.

#### 10.6.6 Apheresis Summaries

For all the subjects who were treated by apheresis at least once during the study, the number and proportion of subjects will be summarized by the type of change (**change in method of apheresis**, change in frequency, change in method, discontinuation of apheresis, first-time initiation of apheresis, re-initiation of apheresis, missed/skipped apheresis procedure and **other**) and primary reason of change.

Statistical Analysis Plan: 20110271

Dated: 26 May 2018 Page 20 of 27

#### 10.7 Other Safety Analyses

#### 10.7.1 Laboratory Test Results

Descriptive statistics will be provided for actual values and changes from baseline in each laboratory parameter at each protocol-specified scheduled visit. Laboratory analytes are provided in the protocol Table 3. Lab shift tables using the most current version of the CTCAE version 4.0 (Appendix B) grading will be used for the following analytes of interest:

- Glucose (hypoglycemia and hyperglycemia)
- Total bilirubin (blood bilirubin increased)
- ALP (alkaline phosphatase increased)
- AST (SGOT) (aspartate aminotransferase increased)
- ALT (SGPT) (alanine aminotransferase increased)
- INR (INR increased)
- Platelets (platelet count decreased)
- WBC/Leukocytes (white blood cell decreased and leukocytosis)
- Neutrophils (neutrophil count decreased)

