7.1.2 Enrollment (EOS Parent/Day 1 OL)

Day 1 for this open-label (OL) study and the end of study visit for the parent study should occur on the same day. All efforts should be made to minimize any time gaps between the parent study EOS and Day 1 in the OL study. The Day 1 OL visit will need to occur within 1 month of the parent EOS or the subject will need to undergo screening procedures ([Section 7.1.1](#)) prior to enrollment. The following procedures will be performed during the end of study (EOS) visit in the parent study and at the Day 1 visit for all subjects that completed screening procedures:

- Vital signs: sitting blood pressure (BP), heart rate (HR)
- AEs/ ADEs/SAEs

- Concomitant medications
- Physical exam for subjects that did not undergo screening
- Body weight for subjects that did not undergo screening
- Measurement of height, weight, and Tanner stage for adolescent subjects (see the [study glossary](#) for definition of adolescence and [Appendix E](#) for guidance on Tanner staging). If Tanner staging cannot be performed on Study Day 1, it should be performed along with height and weight at the next scheduled study visit.
- Documentation of historical assessments of height, weight and Tanner stage for adolescent subjects (see the [study glossary](#) for definition of adolescence and [Appendix E](#) for guidance on Tanner staging). If documentation of historical assessments cannot be obtained on Study Day 1, it should be done as soon as possible after enrollment
- 12-lead electrocardiogram (ECG) in triplicate using centralized ECG services equipment for subjects that did not undergo screening
- Blood draw for serum pregnancy (females of childbearing potential only) and FSH (for applicable subjects)
- Urinalysis
- Blood draw for fasting lipids (≥ 9 hour fasting sample), ApoA1, ApoB, chemistry, coagulation, hematology, PK (AMG 145; PCSK9), hsCRP, Lp(a), biomarkers, and anti-AMG 145 antibodies
- IP administration

Day 1 - subjects will have the risks and benefits of participating in this study explained to them. Subjects that meet inclusion/exclusion criteria will need to sign a new OLE informed consent form, if they already have not done so, before AMG 145 study drug is administered at the site.

Below are additional analytes, not collected during the parent study's EOS visit that will need to be collected for all subjects at Day 1:

- Fasting Vitamin E
- HbA1c

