10.4 Planned Methods of Analysis

10.4.1 General Approach/Considerations

Statistical analyses in this open label study are descriptive in nature. No statistical inference or missing value imputation is planned. **The final analysis for the study will be performed at the end of the study (defined as when the last subject has completed the assessments for week 260 or until the investigator's recommendation of discontinuation, Amgen's recommendation of discontinuation, the subject's decision to discontinue for any reason, or until an administrative decision is made to close the study).**

Subject disposition, demographics and baseline characteristics will be summarized.

Summary statistics for continuous variables will include the number of subjects, mean, median, standard deviation or standard error, minimum, and maximum. For categorical variables, the frequency and percentage will be given.

Subjects will be summarized according to whether subject rolled over from a parent study and their treatment allocation from a parent study when applicable.

For efficacy analyses, the baseline value is defined as:

- Subjects that participated in a qualifying parent study (including 20110233) and with baseline data from the parent study: the baseline is defined as the baseline of the qualifying parent study
- Subjects not enrolling from a parent study or without baseline data from the parent study: the baseline is defined as the baseline in this study

For non-efficacy analyses, baseline values for all subjects are defined as this study baseline values.

The percent change and absolute change from baseline in laboratory based exploratory endpoints at each scheduled visit will be summarized. Summaries of vital signs, ECGs, and anti-AMG 145 antibodies will be also provided.

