#### 6.1 Study Time Points

# **Baseline**

For parent study rollover subjects, baseline is defined as the baseline of the parent study.

For non-parent study subjects, baseline is defined as the time period before the first administration of AMG 145. In particular, for non-parent apheresis subjects, if an assessment was done both pre- and post-apheresis, only the assessment made pre-apheresis will be considered baseline.

Statistical Analysis Plan: 20110271

Dated: 26 May 2018 Page 10 of 27

For hemoglobin A1c, baseline is defined as the study 20110271 baseline for all subjects, as hemoglobin A1c was not collected in study 20110233.

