## 9.3 Handling of Missing and Incomplete Data

## 9.3.1 Patterns of Missing Data

Subjects may be missing specific data points for various reasons. In general, data may be missing due to a subject's early withdrawal from study, a missed visit, or non-evaluability of a data point or an endpoint at a particular point in time. In the Data Quality Review (DQR) process, queries will be made to the sites to distinguish true missing values from other unknown values (eg, due to measurement or sample processing error). All attempts will be made to capture missing or partial data for this trial prior to the database lock for the final analysis.

The frequency and pattern of missing data for endpoints will be assessed through descriptive summaries of the measurements over time. There will be no imputation for missing data.

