# 11. Changes From Protocol-specified Analyses

The protocol specifies treatment-related adverse events will be tabulated by system organ class and preferred term for each treatment arm. This tabulation will not be included in the primary analysis. Instead treatment-related adverse events will be included in the overall adverse event summary and a tabulation of events of interest will be included.

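### SAP 6.1 gives rollovers a parent-study baseline for safety changes, against the protocol and undeclared, and the week 260 vitamin E sample has no row of its own

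*SAP*

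**What the plan says.** SAP Section 10.7.1, under other safety analyses, commits to the following: "Descriptive statistics will be provided for actual values and changes from baseline in each laboratory parameter at each protocol-specified scheduled visit". It takes its analytes from protocol Table 3, which includes fasting vitamin E. Vitamin E is also on the list in SAP Section 10.4, where "All baseline tables will be summarized by study cohorts for all subjects". SAP Sections 10.7.2 and 10.7.3 add changes from baseline for vital signs and ECG intervals.

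On baseline, SAP Section 6.1 states: "For parent study rollover subjects, baseline is defined as the baseline of the parent study". It makes one exception: "For hemoglobin A1c, baseline is defined as the study 20110271 baseline for all subjects, as hemoglobin A1c was not collected in study 20110233". Protocol Section 10.4.1 reserves the parent-study baseline for efficacy and then states: "For non-efficacy analyses, baseline values for all subjects are defined as this study baseline values". The only departure that SAP Section 11 declares concerns adverse events: "The protocol specifies treatment-related adverse events will be tabulated by system organ class and preferred term for each treatment arm".

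On timing, protocol Section 7.1.2 names two analytes, fasting vitamin E and HbA1c, as "not collected during the parent study's EOS visit that will need to be collected for all subjects at Day 1". Section 7.1.2.5 schedules vitamin E at weeks 12, 24, 48, 72 and 96, and Section 7.1.2.6 schedules it again at the week 260/early termination visit. In SAP Appendix A, the vitamin E column of Table A.1 ends with a week 96 row that is open from day 589. Table A.3, which covers assessments made only at the end of study, does not list vitamin E.

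**The concern.** The primary objective is long-term safety, so safety changes should start from the time point the protocol sets, and the last scheduled value should be reported under its own visit.

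The baseline rule reaches every non-efficacy change-from-baseline value in rollovers; vitamin E is one case. For that analyte there is a further risk. If a parent study did not measure it at baseline, its rollovers have no change value at all: SAP Section 6.1 has no fallback, and Section 9.3.1 says "There will be no imputation for missing data". The mandatory Day 1 value would then not serve as a baseline.

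The window rule concerns vitamin E only. The end-of-study draw is its sole scheduled measurement after week 96. As the table stands, that value is either left out or reported under a visit about three years earlier.

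**Working it through.** **Baseline: the rules side by side**

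- Protocol 10.4.1, efficacy: parent-study baseline for rollovers who have one; otherwise this study's baseline.
- Protocol 10.4.1, non-efficacy: this study's baseline for all subjects.
- SAP 6.1: parent-study baseline for rollovers, with no split between efficacy and safety and no fallback. HbA1c is the only exception.
- SAP 11: no mention of a change in baseline.

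The SAP therefore contradicts the protocol for rollovers' changes in chemistry, hematology, coagulation, vitamin E, vital signs and ECG. For vitamin E there are two branches. If a parent baseline was measured, the change runs from a time point that the protocol does not set. If not, there is no change value. The documents do not show which branch applies.

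The number of rollovers is not given. Study 20110233 planned 59 subjects (protocol Section 2.2.4). If all entered, that is 59/310 = 19.0% of the planned sample. Other qualifying parent studies would add to this, and the share within an apheresis cohort may differ, so 19% is an illustration and not a bound.

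**Vitamin E windows: reproducing Table A.1**

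Scheduled day = 7 × week + 1. For weeks 12, 24, 36, 48, 72 and 96 this gives 85, 169, 253, 337, 505 and 673, as printed. The midpoints between neighbouring rows are:

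- (85 + 169)/2 = 127
- (169 + 253)/2 = 211
- (253 + 337)/2 = 295
- (337 + 505)/2 = 421
- (505 + 673)/2 = 589

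These reproduce every lower bound from week 24 to week 96. The week 96 row has no upper bound because no row follows it.

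**Placing the week 260 sample**

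- Week 260 = 7 × 260 + 1 = day 1821. The only vitamin E window that holds it is week 96.
- Distance from target: 1821 − 673 = 1148 days = 164 weeks (1148/365.25 = 3.1 years).
- The largest possible distance in the other rows is 83 days (week 12), 42 (week 24), 42 (week 36), 83 (week 48) and 84 (week 72).

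**What the record-selection rule does**

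- Week 96 record present: the record closest to day 673 is kept. Even with both visits 7 days off schedule, the distances are 680 − 673 = 7 and 1814 − 673 = 1141. The week 260 value appears in no row.
- Week 96 record absent: the day 1821 value, or any early-termination value from day 589 onward, is reported as week 96.
- Apheresis subjects: Appendix A gives priority to a record taken on an apheresis day. If the week 96 sample was not taken on such a day and the end-of-study sample was, the later one replaces a true week 96 value.

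**Comparison within the same table**

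The chemistry row for n = 264 runs from (264 − 6) × 7 + 1 = 1807 to (264 + 6) × 7 = 1890, and the last antibody window starts at day 1639. Both hold day 1821, although they are labelled week 264. Only the vitamin E column leaves a scheduled end-of-study draw without a late row.

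**The case against.** Five arguments carry weight.

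First, a parent-study baseline precedes parent-study drug, so for rollovers who were on AMG 145 it may be the more informative reference. Protocol Section 10.4.2.3 even describes the baseline for laboratory shift tables as the start of AMG 145 exposure. This stands as a scientific argument. It would support a declared departure with a fallback, but not a silent one that covers all safety changes.

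Second, SAP 6.1 justifies the HbA1c exception by saying that HbA1c was not collected in study 20110233. Naming HbA1c alone hints that vitamin E was collected there. A reader might infer the opposite, that rollovers certainly lack a vitamin E baseline, because protocol Section 7.1.2 pairs the two analytes. The documents support neither inference: that section speaks only of the parent end-of-study visit.

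Third, the footnotes to the three schedules in protocol Appendix A limit vitamin E to Day 1 and weeks 12 to 96, which could mean that no end-of-study sample is planned. However, the footnotes are attached to the Day 1 and quarterly cells. The end-of-study cell carries a plain mark, and Section 7.1.2.6 lists the test.

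Fourth, a reader might conclude that the vitamin E rows as a whole are unusable. They are not. Actual values at weeks 12 to 72 are sound for everyone, as are non-rollover changes at those weeks, and the week 96 row usually keeps the true week 96 sample.

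Fifth, it is tempting to count how many end-of-study values are lost or mislabelled. That needs retention and missed-visit rates, which the documents do not give.

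**Conclusion.** Both defects hold as written, and both are minor.

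The baseline conflict is general. It affects rollovers' changes from baseline in all safety laboratory parameters except HbA1c, and in vital signs and ECG. It follows from the text alone. The stronger statement, that rollovers have no vitamin E change value, is conditional on vitamin E not having been measured at the parent baseline.

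The window gap is specific to vitamin E. The week 260 sample lies 1148 days past the only target available to it. It is normally dropped when a week 96 record exists, is reported as week 96 when none does, and in some apheresis subjects may displace a true week 96 value. This rests only on the protocol schedule and the Appendix A rules.

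No inference is planned, vitamin E is not a named endpoint, and the primary endpoint is unaffected.

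**What to change.** **SAP Section 6.1.** Limit the parent-study baseline to efficacy analyses. For all non-efficacy parameters and all subjects, define baseline as the last study 20110271 value before the first dose in this study. State that parent end-of-study assessments that double as Day 1 count as such values. Add a footnote that Day 1 is an on-drug value for rollovers who received AMG 145 in the parent study.

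**SAP Table A.1, vitamin E column.** Close week 96 at days 589-756. This is 673 − 84 to 673 + 83, the pattern already used for week 72 (505 − 84 = 421 to 505 + 83 = 588). Add an end-of-study/early-termination row for samples from day 757 onward. Up to week 260 that row spans 1821 − 757 = 1064 days, so either summarise study day beside it or show week 260 completers apart from early terminations.

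**Cost.** A few sentences, one window limit, one row and one footnote; the Day 1 and end-of-study draws are already scheduled. The downside is that change from Day 1 may understate the effect in rollovers already on drug, which is why the footnote is needed.

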## 10.7.2 Vital Signs

Vital signs will be summarized using descriptive statistics at each measurement time point. Systolic and diastolic blood pressure and heart rate will be summarized for each defined group using descriptive statistics at each scheduled visit. Apheresis subjects and non-apheresis subjects will be summarized in separate tables given different time points. Summaries will also include the change from baseline at each scheduled visit.

# 10.7.3 Electrocardiogram

For post-baseline assessments where ECG is performed in triplicate, the average of the 3 (or all available) readings will be used for analysis. Observations with the following diagnosis or findings will be excluded from analysis: artificial pacemaker, atrial fibrillation, atrial flutter, left bundle branch block, and right bundle branch block.

PR, QRS, QT, QTc (ie, QTcB and QTcF) and RR intervals and their change from baseline will be summarized for each group by scheduled visit. In each group, subjects will be categorized and summarized per their maximum post-baseline absolute QTc interval using limits of 450 ms, 480 ms, and 500 ms. They will also be categorized per their maximum change from baseline QTc interval using limits of 30 ms and 60 ms.

Statistical Analysis Plan: 20110271

Dated: 26 May 2018 Page 21 of 27

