7.1.2.6 End of Study (Week 260)/Early Term OL Visit – All Subjects

- Vital signs: sitting blood pressure (BP), heart rate (HR)
- AEs/ADEs/SAEs
- Concomitant medications
- Physical exam
- Measurement of, height, weight, and Tanner stage for adolescent subjects (see the [study glossary](#) for definition of adolescence and [Appendix E](#) for guidance on Tanner staging)
- Body weight
- Blood draw for serum pregnancy (for females of childbearing potential only)
- Blood draw for fasting lipids (≥ 9 hour fasting sample), ApoA1, ApoB, chemistry, hematology, PK (AMG 145), PCSK9, coagulation, hsCRP, Lp(a), HbA1c, fasting Vitamin E, and anti-AMG 145 antibodies
- Urinalysis
- 12 Lead ECG in triplicate using centralized ECG services equipment

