10.4.2.3 Exploratory Safety Analyses

Safety Laboratory Parameters

Laboratory parameters will be summarized using descriptive statistics at each measurement time point. Laboratory shift tables for certain analytes will be provided using the CTCAE v.4 toxicity criteria. The results will be based on the maximum (ie, worst) shift from baseline (starting of the exposure of AMG 145) to the end of study.

Vital Signs

Vital signs will be summarized using descriptive statistics at each measurement time point.

Electrocardiogram

RR, PR, QRS, QT, and QTc intervals will be summarized at each measurement time point. Frequency tables for maximal QTc and maximal change in QTc at post-dose period using the categories suggested in the ICH E14 guidelines will be provided by treatment group.

PK Parameters

Summary statistics of PK concentration and PCSK9 will be provided.

Anti-AMG 145 Antibodies

The incidence and percentages of subjects who develop anti-AMG 145 antibodies (binding and neutralizing) at any time will be tabulated.

Concomitant Medications

Concomitant medications of interest will be summarized.

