Week 16	113	99-126	99-126	99-126
Week 20	141	127-154	127-154	127-154
Week 24	169	155-210	155-210	155-210
Week n	n*7+1	From (n-6)*7+1 to (n+6)*7	From (n-6)*7+1 to (n+6)*7	From (n-6)*7+1 to (n+6)*7

Where n=36, 48, 60 and so on, incremental by 12, until 264. a Lipid panel excluding Direct VLDL and Direct LDL.

Table A.3 Visit Window for Endpoints Collected only at the End of Study

Scheduled Visit Week	Weight, Physical Exam, Urinalysis, 12 Lead ECG,eGFR
EOS	>1

Statistical Analysis Plan: 20110271

Dated: 26 May 2018 Page 26 of 27

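### The ECG exclusion in SAP 10.7.3 also applies to QRS, so new bundle branch block is removed from the QRS summary and counted in no ECG table (minor)

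*SAP*

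**What the plan says.** SAP 10.7.3 opens with the averaging rule: "For post-baseline assessments where ECG is performed in triplicate, the average of the 3 (or all available) readings will be used for analysis". The exclusion follows directly: "Observations with the following diagnosis or findings will be excluded from analysis: artificial pacemaker, atrial fibrillation, atrial flutter, left bundle branch block, and right bundle" (ending with right-sided block). The next sentence names what is analysed: "PR, QRS, QT, QTc (ie, QTcB and QTcF) and RR intervals and their change from baseline will be summarized for each group by scheduled visit". The only categorical ECG output is for QTc: "subjects will be categorized and summarized per their maximum post-baseline absolute QTc interval using limits of 450 ms, 480 ms, and 500 ms", together with limits on the QTc change from baseline.

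Protocol 10.4.2.3 has the same set of intervals and mentions no exclusion: "RR, PR, QRS, QT, and QTc intervals will be summarized at each measurement time point".

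On timing, Protocol 7.1.2.6 requires at the end-of-study or early-termination visit: "12 Lead ECG in triplicate using centralized ECG services equipment". SAP Appendix A places ECG in "Table A.3 Visit Window for Endpoints Collected only at the End of Study", in the row headed "Weight, Physical Exam, Urinalysis, 12 Lead ECG,eGFR", with a window of any day after Day 1.

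**The concern.** The primary objective is to characterise long-term safety. Leaving these tracings out of a QTc summary is ordinary practice, because QTc is hard to interpret in them. PR cannot be measured in atrial fibrillation or flutter. QRS is different. By the general ECG definition (the documents do not give it), bundle branch block is recognised by a prolonged QRS. Excluding tracings with block from the QRS summary therefore selects on the outcome: the values dropped are the abnormal ones, and they are dropped because they are abnormal.

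With one scheduled post-baseline ECG per subject, there is usually no second tracing to keep the subject in. A reader of the QRS table would see a maximum without the widest complexes, and would not learn from any ECG output that tracings had been set aside, how many, or whether the finding was new on AMG 145.

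**Working it through.** The plan states no figure on this point to reproduce. The check is mainly a comparison of passages, followed by an illustration on assumed values.

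**1. Scope of the exclusion.** The sentence sits between one about post-baseline ECGs and one listing PR, QRS, QT, QTcB, QTcF and RR. Nothing in it restricts it to QT/QTc or to findings present at baseline. As written, it covers QRS and covers findings that first appear on treatment.

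**2. Number of post-baseline ECGs.**

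| Visit | Source | ECG listed? |
|---|---|---|
| Screening, or Day 1 if not screened | Protocol 7.1.1, 7.1.2 | Yes |
| Weeks 2 to 20 (including week 9 for apheresis) | Protocol 7.1.2.1 to 7.1.2.4 | No |
| Quarterly visits | Protocol 7.1.2.5 | No |
| End of study / early termination | Protocol 7.1.2.6 | Yes |

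The three schedules in Protocol Appendix A agree, and so does SAP Table A.3. There is one scheduled post-baseline ECG. If it carries one of the five findings on all readings, the subject normally has no post-baseline value and no change from baseline for any interval.

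**3. Other ECG output that would show the finding.** SAP 10.7.3 plans no shift table, no PR or QRS category table, no table of qualitative findings and no count of excluded tracings. The QTc categories are subject to the same exclusion.

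**4. What the summary is meant to report.** SAP 10.1 includes the maximum among the statistics for continuous variables, and SAP 9.5 keeps outliers in unless otherwise specified. The QRS maximum is the statistic that the exclusion affects most.

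**5. Illustration.** Only N = 310 (Protocol 3.3) comes from the documents. Assumed: every subject has an end-of-study ECG; new bundle branch block in 0.5% to 3% of subjects; QRS widening of 30 to 50 ms in those; no change in the others.

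With k affected subjects and widening d, the mean change with all tracings kept is k × d / 310.

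| Assumed incidence | k | Mean at d = 30 ms | Mean at d = 50 ms | N left under the SAP rule |
|---|---|---|---|---|
| 0.5% | 2 | 2×30/310 = 0.19 | 2×50/310 = 0.32 | 308 |
| 1% | 3 | 3×30/310 = 0.29 | 3×50/310 = 0.48 | 307 |
| 2% | 6 | 6×30/310 = 0.58 | 6×50/310 = 0.97 | 304 |
| 3% | 9 | 9×30/310 = 0.87 | 9×50/310 = 1.45 | 301 |

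Under the SAP rule the mean change is 0 in every row, so it differs from the full-data mean by about 0.2 to 1.5 ms. The maximum change is 30 to 50 ms with all tracings kept and 0 with the exclusion. The number of subjects shown with block-range QRS widening is 2 to 9 against none.

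**The case against.** The strongest reply is that ECG intervals are supporting data and that the main safety route is open. They are not listed as endpoints in Protocol 10.1.3 or SAP 4.3, and the study is descriptive, single-arm and without inference. A new block, arrhythmia or pacemaker can be reported as an adverse event under the broad definition in Protocol 9.1.1, and treatment-emergent events are the primary endpoint, tabulated under SAP 10.5.1. All of this stands, and it keeps the point minor. It does not close the gap: reporting rests on the investigator, and no text says that a new finding on the final ECG must be entered as an event.

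It can also be said that the rule acts on observations, a term the SAP does not define. If it means a single reading, an unaffected reading in the triplicate could remain. Because the Table A.3 window is open-ended, an unscheduled ECG could also count. Both are possible, which is why loss of the subject is the normal result of a persistent finding and not a certain one. In either case the tracing with block still leaves the QRS summary.

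Three stronger readings are tempting, and the documents do not support them:

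- **That the rhythm and PR results are distorted in the same way.** SAP 10.7.2 summarises heart rate and its change at each scheduled visit with no rhythm exclusion, and PR is not measurable in fibrillation or flutter.
- **That every subject with worsening conduction disappears.** PR prolongation, or QRS widening without one of the five findings, stays in the tables.
- **That a drug effect on QRS is being hidden.** There is no control group against which such an effect is estimated, and on the assumed values the mean hardly moves.

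**Conclusion.** The point holds for QRS and for the missing counts. As written, the exclusion removes QRS values because of the abnormality that QRS is there to show, and no planned ECG output records that this happened. The loss lies in the QRS maximum and in the number of affected subjects. Its actual size cannot be derived, because the documents give neither an incidence of new block nor a degree of widening; the 2 to 9 subjects and 0.2 to 1.5 ms above depend on the stated assumptions. The exclusion for QT/QTc, and for PR in fibrillation or flutter, is sound.

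A reader might also infer an undeclared departure from the protocol, since SAP Section 11 does not mention the exclusion. That goes too far. All the intervals are still summarised, and the rule can be read as detail added to the protocol's analysis. Severity: minor.

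**What to change.** In SAP 10.7.3:

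1. Limit the exclusion to QT, QTcB and QTcF, and to PR where it cannot be measured. Keep bundle-branch-block tracings in the QRS summary.
2. Report, for each of the five findings, the number of subjects with excluded tracings, split into present at baseline and new at end of study or early termination. Use the number of subjects with an evaluable ECG as denominator, where evaluable means that a usable tracing was recorded, not that it escaped the exclusion.

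While editing, say whether an observation is one reading or the averaged triplicate. Listing the exclusion in Section 11 is optional tidying.

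The cost is a wording change and one short table or footnote. No new data are needed, because applying the exclusion already requires the ECG diagnoses. The downside is small: the QRS summaries become slightly more variable and slightly less favourable.
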